#### 10.2.3 Descriptive Analysis

Independently of results on primary and key secondary endpoints, descriptive in nature analyses will be performed on all secondary endpoints (section 3.2.2) at each available timepoints by means of descriptive statistics.

In case of continuous measures, analyses will be provided for baseline visit, each post-baseline visit, and their change from baseline. Comparisons between treatments will be performed using twosample t-test (assuming unequal variances) or, if the required assumptions are not met, the two-

sample Mann–Whitney U test will be used. Assumption of normal distribution of endpoints for continuous data will be assessed by a visual inspection of distribution.

In case of categorical variables, shift tables versus baseline will be summarized for all post-baseline visits, and the Fisher's Exact test will be performed.

The following graphical representations will be provided by treatment:

- Schirmer I test Observed Mean (±SEM) and Mean change from baseline (±SEM) at each timepoint.
- Observed percentage of patients with Schirmer I test >10mm/5min at each timepoint.
- SANDE global score Observed Mean (±SEM) and Mean change from baseline (±SEM) at each timepoint.
- Cornea and conjunctiva vital staining total score Observed Mean (±SEM) and Mean change from baseline (±SEM) at each timepoint.
- TFBUT Observed Mean (±SEM) and Mean change from baseline (±SEM) at each timepoint.

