#### 3.2.1 Primary

| Objective(s)   | Endpoint(s)   |
|--|---|
| • To compare the efficacy of cenegermin vs.
vehicle in Schirmer I test (without anesthesia)
>10mm/5min at week 4 by testing the
superiority.          | • Schirmer I test (without anesthesia) >10mm/5min at week 4.                  |
| • To compare the efficacy of cenegermin vs. vehicle in Symptom Assessment in Dry Eye questionnaire (SANDE) global score at week 12 by testing the superiority. | • Change from baseline in SANDE global score at week 12                       |
| 3.2.2 Secondary  |   |
| Objective(s)   | Endpoint(s)   |
| • To compare the efficacy of cenegermin vs. vehicle in Schirmer I test at week 4, 8, 12 and 16 by testing the superiority.                                     | • Change from baseline in Schirmer I test [Time frame: week 4, 8, 12 and 16]. |

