# 5. Sample size justification

The sample size of the study is calculated based on results from previous studies.

Sample size was calculated according to the following assumptions:

- randomization ratio 1:1.
- a difference of 42% in Schirmer I rate of responders (value >10mm/5min at week 4.) in favor of rhNGF treatment at Week 4, with a responder rate of 33% for vehicle.
- 10 points in Global SANDE score improvement at Week 12, with a standard deviation of 12 points.

Based on these assumptions, a total sample size of 72 evaluable patients (80 pts considering 10% of patients not evaluable after enrollment) allows to achieve an overall power of 90% to show superiority of rhNGF eye drops solution vs vehicle in terms of primary endpoint, considering a one-sided alpha of 0.025.

Specifically:

- A power of 96.3% is achieved for Schirmer I primary endpoint.
- A power of 94.1% is achieved for SANDE primary endpoint.

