### 7. Statistical Analysis

### 7.1 General

All patient data collected during the study will be listed by patient and site.

Appropriate descriptive statistics will be produced by treatment arms according to the nature of the variable.

For continuous data, number of observations, mean, standard deviation, median, Q1-Q3, range (minimum and maximum) and 95% confidence intervals will be presented.

For categorical data, frequency distributions and percentages with 95% confidence intervals (Wilson method) per category will be presented.

For primary analysis, the threshold for claiming statistical significance will 0.025 one-sided. For other analysis, unless otherwise specified, the significance level for statistical testing will be 0.05 and two-sided tests.

The statistical analyses (both descriptive and inferential) of some endpoints will be done on the eligible eye when applicable. Details will be provided in the statistical analysis outputs as notes.

Additional post-hoc analysis may be produced to further allow comparison between treatment and control, according to the results obtained. Any deviations from the original statistical plan (including unplanned analyses) will be documented in the CSR.

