If there are not enough retrieved dropouts for convergence of MI-RD regression model, a referencebased Multiple Imputation (MI) approach will be adopted to consider a missing not at random (MNAR) mechanism for missing data: imputation of values in the rhNGF arm (above step #2) will be done using the non-missing values from the control group (this approach will be referred as "Copy Reference"). This approach does not assume benefits for rhNGF in case of discontinuation and limits a post-discontinuation clinical effect to that of vehicle. The final decision on the use of the MI-RD vs Copy-Reference for this endpoint will be done at the time of the analysis and reported in the CSR.

Whether for MI-RD or Copy-Reference approach, the adjusted estimated treatment differences in proportions between cenegermin and vehicle at week 4 will be displayed together with the corresponding two-side 95% confidence intervals and p-value.

### 10.1.2.2 Change from baseline in the global SANDE score at week 12

This co-primary endpoint will be analyzed by means of an Analysis of Covariance (ANCOVA) adjusting by pre-defined baseline factors (gender, age class, baseline global SANDE score as fixed effects and site as random effect) and a one-sided test will be used to test for differences between treatment groups. Rules for derivation of SANDE scores are reported in section 12.2.

For the imputation of missing data, a regression model will be created by including the baseline global SANDE score, gender, age class, and intermediate global SANDE scores up to week 12. Two hundred data sets will be generated, and the random seed number will be 252404. MI will be implemented in the following steps:

- 1. Partial imputation assuming MAR will be carried out to impute intermittent (non-monotone) missing data of global SANDE score based on a multivariate joint Gaussian imputation model using the MCMC method. A separate imputation model will be used for each treatment arm. In case of non-convergence or non-estimability issues, a single imputation model will be considered (with treatment arm added as explanatory variable to the model). A total of 200 datasets will be created. These datasets will be utilized in Step #2.
- 2. The remaining monotone missing data will be imputed using a MI regression including the same explanatory variables of the previous step. According to MI-RD approach, only non-missing values from retrieve dropouts will be used to inform the regression model.

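### Change in Schirmer I, SANDE at weeks 8 and 16, and NEI, TFBUT and IDEEL at week 16 are compared only by unadjusted tests: a small, avoidable loss of precision

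*SAP*

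**What the plan says.** SAP 10.2.3 covers every secondary endpoint at every available visit, whatever the primary and key secondary results, and labels these analyses descriptive. For continuous measures: "Comparisons between treatments will be performed using twosample t-test (assuming unequal variances", or a Mann-Whitney test if assumptions fail. Categorical measures get Fisher's exact test. No covariate is named. SAP 7.1 sets the level: "For other analysis, unless otherwise specified, the significance level for statistical testing will be 0.05 and two-sided tests".

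The objectives in SAP 3.2.2 are worded more strongly. For Schirmer I the objective reads "To compare the efficacy of cenegermin vs. vehicle in Schirmer I test at week 4, 8, 12 and 16 by testing the superiority", and NEI, TFBUT, SANDE and IDEEL have parallel wording.

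Adjusted models exist for part of this list:
- SANDE global score at week 12 (SAP 10.1.2.2) has an ANCOVA with "gender, age class, baseline global SANDE score as fixed effects and site as random effect". SANDE severity and frequency at week 12 follow it.
- Schirmer I is modelled only as a responder (>10 mm/5 min) at weeks 4 and 8, by logistic regression with baseline and site.
- IDEEL, NEI and TFBUT have MMRMs (SAP 10.2.2.4 to 10.2.2.6) with gender, age class and baseline but without site. Their tables run up to week 12.

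Randomization is stratified by site (SAP 6.1.1). Protocol 9.4.3.3 asks only for suitable parametric tests in the descriptive analyses.

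**The concern.** Subtracting the lists leaves these comparisons with an unadjusted test and nothing else: change in Schirmer I at all four visits, SANDE scores at weeks 8 and 16, and NEI, TFBUT and IDEEL at week 16. Change in Schirmer I is the first-listed secondary endpoint and was the primary endpoint of the phase II trial described in Protocol 2.2.

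Two things are at stake. The first is precision: with about 40 patients per arm, a raw change score carries chance baseline imbalance and more variance than it need. The second is consistency: SANDE global score at week 12 comes from a model adjusted for baseline and site after multiple imputation, while weeks 8 and 16 come from raw comparisons. SAP 7.8 reserves multiple imputation for the primary and key secondary analyses. The change-from-baseline tables (14.2.5.1, 14.2.5.2, 14.2.5.4 to 14.2.5.6) are also part of the key first results, whereas the adjusted key secondary tables (14.2.4) are not. If the 10.2.3 tests are printed there, they will be the first secondary comparisons seen.

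**Working it through.** **The plan's own figures.** SAP 5 gives "randomization ratio 1:1", "a total sample size of 72 evaluable patients (80 pts considering 10% of patients not evaluable after enrollment", "a difference of 42% in Schirmer I rate of responders" with 33% on vehicle, and 10 points with SD 12 for SANDE, "considering a one-sided alpha of 0.025". With 36 per arm:
- SANDE: 10 / (12 × √(2/36)) = 3.536; Φ(3.536 − 1.960) = 94.2% (stated 94.1%; noncentral t gives 93.7%).
- Schirmer I, 75% against 33%: pooled SE = √(2 × 0.54 × 0.46/36) = 0.1175; unpooled SE = √((0.75 × 0.25 + 0.33 × 0.67)/36) = 0.1065; Φ((0.42 − 1.960 × 0.1175)/0.1065) = 96.3% (stated 96.3%).
- 72/0.90 = 80.

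These reproduce. The documents give no power or precision figure for the 10.2.3 comparisons, so the rest uses assumed ranges.

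**Baseline adjustment.** Let s0 and s1 be the baseline and follow-up SDs, k = s0/s1, and r their correlation. The variance of a raw change is s1²(1 + k² − 2rk). The ANCOVA residual variance is s1²(1 − r²). In large samples the ratio is (1 − r²)/(1 + k² − 2rk). Denominator minus numerator is (k − r)², so ANCOVA is never worse and the two are equal when r = k. The interval narrows by 1 − √ratio.

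**Inputs.** Entry limits Schirmer I to 2-5 mm. Its baseline SD is therefore 3/√12 = 0.87 mm if uniform and at most 3/2 = 1.5 mm. Follow-up SD is assumed at 4 to 10 mm. As a plausibility check, a normal vehicle distribution with 33% above 10 mm has SD (10 − mean)/0.44, which is 4.5 to 9.1 mm for means of 8 down to 6 mm. For SANDE-type scores, k = 0.8 to 1 and r = 0.3 to 0.7 are assumed.

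Variance ratio, adjusted to unadjusted:

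| Score | s0/s1 | r = 0 | r = 0.3 | r = 0.5 | r = 0.7 |
|---|---|---|---|---|---|
| Schirmer I | 0.87/10 | 0.992 | 0.953 | 0.815 | 0.576 |
| Schirmer I | 0.87/6 | 0.979 | 0.974 | 0.856 | 0.623 |
| Schirmer I | 1.5/6 | 0.941 | 0.997 | 0.923 | 0.716 |
| Schirmer I | 1.5/4 | 0.877 | 0.994 | 0.980 | 0.828 |
| SANDE-type | k = 0.8 | – | 0.784 | 0.893 | 0.981 |
| SANDE-type | k = 1 | – | 0.650 | 0.750 | 0.850 |

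- SANDE-type: ratio 0.65 to 0.98. Intervals are 1 − √0.981 = 1% to 1 − √0.650 = 19% narrower, and 72 patients act like 73 to 111.
- Schirmer I, r from 0 to 0.3: ratio 0.88 to 1.00, intervals 0 to 6% narrower, and 72 patients act like 72 to 82.
- Schirmer I, r = 0.5: 1 to 10% narrower. At r = 0.7 it would be 9 to 24%, but so narrow an entry range makes a correlation that high unlikely.

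In power terms, a comparison with 80% power unadjusted would have Φ(2.80/√ratio − 1.96): 80.4% at a ratio of 0.99, 84.0% at 0.90 and 89.9% at 0.75.

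**Site.** Under site-stratified randomization, removing between-site variance multiplies the variance by 1 − ICC. The unadjusted test then has true two-sided level 2(1 − Φ(1.96/√(1 − ICC))). For assumed ICCs of 0.02, 0.05 and 0.10, variance falls by 2, 5 and 10% and the true level is 0.048, 0.044 and 0.039. The test is conservative, not inflated.

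**The case against.** Nothing confirmatory rests on these tests. Section 10.2.3 is descriptive, the co-primary and hierarchical results come from adjusted models, and a simple test is a legitimate choice for a descriptive table that Protocol 9.4.3.3 allows. The section also gives one unadjusted series per scale across all visits, so a like-for-like reading over time is possible. Week 16 differs anyway, because other topical treatments are permitted after week 12. All of this stands and keeps the point minor. It does not explain why endpoints with superiority objectives should go without an adjusted estimate when the covariates are collected.

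Three stronger readings are tempting, and the documents do not support them:
- A reader might infer that all other analyses adjust for both baseline and site. The IDEEL, NEI and TFBUT MMRMs leave site out.
- A reader might infer that every visit outside weeks 4 and 12 lacks an adjusted estimate. NEI and TFBUT at week 8 are in the hierarchy, and the IDEEL MMRM reports each visit up to week 12. For these scales only week 16 is missing.
- A reader might carry the equal-variance result, ratio (1 + r)/2, over to Schirmer I. At r = 0.3, 0.5 and 0.7 it implies 54, 33 and 18% more patients for the same precision (1/0.65, 1/0.75, 1/0.85). Equal variances do not fit a baseline confined to 2-5 mm. Chance imbalance there is small too: with 40 per arm, the SE of the baseline difference is 0.87 × √(2/40) = 0.19 mm to 1.5 × √(2/40) = 0.34 mm.

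**Conclusion.** The point holds as a minor one about efficiency and consistency. The gap is confined to the endpoints and visits named in the heading. The direction is certain in large samples; the size is not, because correlations, follow-up SDs and the site ICC are all assumed. SANDE at weeks 8 and 16 has the most to gain under those assumptions. For change in Schirmer I the gain is probably slight, and the better argument is that this endpoint would otherwise have no modelled estimate at all. The unadjusted tests remain valid.

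**What to change.** In SAP 10.2.3, make the between-arm comparison for change in Schirmer I (weeks 4, 8, 12, 16), SANDE scores (weeks 8 and 16) and NEI, TFBUT and IDEEL (week 16) an ANCOVA on change. Use treatment, baseline value, gender and age class, with site as a random effect, following the SANDE week 12 model. For NEI, TFBUT and IDEEL the alternative is to extend the MMRMs to week 16 and add site. Report the adjusted difference with its 95% confidence interval, say whether the models use observed or imputed data, and keep the t-test or Mann-Whitney test as a supplementary summary.

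The cost is low but not nil. The SANDE ANCOVA code in SAP 15.4.2 can be adapted. A model for continuous Schirmer change has to be written, since none exists, and site has to be added if the MMRM route is taken. A few tables are added, no new data are needed, and the results keep their descriptive status.

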# 11. Evaluation of Safety

#### **11.1** Adverse events

Adverse Events (AEs) started before administration of study treatment will be considered as pretreatment; any AE started on or after the date of the first dose of study medication or started prior to first dose and worsened in severity after the first dose will be considered as Treatment-Emergent Adverse Event (TEAE).

In case of missing or incomplete dates not allowing a direct allocation to any of the two categories of AEs (pre-treatment/TEAE), an allocation will be done according to the available parts of the onset and the end dates (see Table 6). In case of TEAE, the event can be further classified as:

- On Treatment period, or
- On Follow-up period

according to the available parts of the onset and the end dates (see Table 6).

All AEs will be coded by SOC and PT according to MedDRA thesaurus. In addition, each AE will be graded to capture the relationship to IMP and severity (see protocol for details).

Pre-treatment AEs will be presented in the listings only.

TEAE summaries will be presented, displaying frequencies and percentages of patients reporting AEs within each SOC in decreasing order of total frequency. Along with AEs, number of events will be reported. On each of these summaries, patients will be counted only once per SOC and, withing each SOC, patients will be counted only once per PT.

"Possible", "Probable" and "Highly Probable" or missing relationships will be considered as related to study drug (ADR – Adverse Drug Reaction) for the summary tables. "None" and "unlikely" relationships will be considered not related to study drug.

The following table will be presented by treatment group and overall:

- A summary overview (patient with at least one event, percentage, and number of events) of:
  - o TEAEs,
  - Ophthalmic TEAEs,
  - Non-Ophthalmic TEAEs,
  - o severe TEAEs,
  - o severe Ophthalmic TEAEs,
  - o severe Non-Ophthalmic TEAEs,
  - o serious TEAEs,
  - o serious Ophthalmic TEAEs,
  - o serious Non-Ophthalmic TEAEs,
  - o non-serious TEAEs,
  - o ADRs,
  - Ophthalmic ADRs,
  - Non- Ophthalmic ADRs,
  - o serious ADRs,
  - TEAEs leading to discontinuation of IMP,
  - TEAEs leading to discontinuation of study,
  - TEAEs leading to death.

The following tables will be presented by treatment group:

- Summary of Ophthalmic TEAEs by primary SOC and PT and by study period (on treatment/follow-up and overall).
- Summary of Non-Ophthalmic TEAEs by primary SOC and PT and by study period (on treatment/follow-up and overall).
- Summary of TEAEs by primary SOC, PT and Severity.
- Summary of Serious TEAEs by Primary SOC and PT and by study period (on treatment/follow-up and overall).
- Summary of ADRs by Primary SOC and PT and by study period (on treatment/follow-up and overall).
- Summary of ADRs by Primary SOC and PT and Severity.
- Summary of TEAEs leading to IMP Discontinuation by Primary SOC and PT and by study period (on treatment/follow-up and overall).
- Summary of TEAEs leading to study Discontinuation by Primary SOC and PT and by study period (on treatment/follow-up and overall).
- Summary of TEAEs leading to Death by Primary SOC and PT.
- Listing of Deaths.

#### 12. Derivations and date conventions

# 12.1 Variable derivation

#### Table 3: Variable derivation rules

| Parameter   | Calculation  |
|---|--|
| Screened  | A patient is considered screened if (s)he has "Has written Informed Consent been obtained?" = Yes AND "Date of Informed Consent Signature at screening" filled   |
| Screening failure   | A patient is considered screening failure if (s)he has "Screen Failure date" filled  |
| Enrolled  | A patient is considered enrolled if (s)he has been screened and (s)he is not a screening failure.  |
| Eligible eye  | Assuming that all the inclusion/exclusion criteria are met:  |
|   | 
 
If only one eye fulfills the criteria of Severe Sjögren's Dry Eye ("Which eye is diagnosed with Severe Sjögren's Dry Eye?" is answered with "Right Eye" or "Left Eye") than the selected eye will be the "eligible eye".
 
If both eyes fulfill the criteria of Severe Sjögren's Dry Eye ("Which eye is diagnosed with Severe Sjögren's Dry Eye?" is answered with "Both") than the eligible eye will be selected according to the following rank: 
 
the eye with lower Schirmer I score, otherwise
 
the eye with worse NEI score (cornea+conjunctival staining), otherwise
 
the eye with worse investigator's judgement ("Were there any clinically significant abnormalities noted?" Equal to yes for a specific eye), otherwise
 
the right eye.
 
 
 
 |
| Change from baseline  | Each change from baseline will be defined as difference between the value at each post-baseline assessment and the baseline value.   |
| Time since first diagnosis of Dry
Eye  | Randomization date - Date of diagnosis for eligible eye + 1  |
| Time since first diagnosis of
Severe Sjögren's Dry Eye                         | Randomization date - Date of diagnosis of Severe Sjögren's Dry Eye for eligible eye + 1  |
| Total number of drops in the
eligible eye taken during the
treatment period | Sum of Morning/Afternoon/Evening Number of times the IMP has been administered for the eligible eye between Randomization visit date and End of Treatment date, considering 1 drop each time (morning, afternoon, evening).  |
| treatment period  | (from the eCRF form "IMP Administration" forms)  |

| Total number of drops in the
eligible eye scheduled during the
treatment period             | 3*(Date of End of Treatment visit – Date of Randomization + 1) – (assessments not done on Randomization visit + assessments not done on End of Treatment visit)  |
|---|--|
| The extent of exposure (days)   | Date of last administration of IMP – Date of first administration of IMP + 1   |
| Total number of drops of the
preservative free artificial tears
during the treatment period | Sum of Morning/Afternoon/Evening Number of drops taken for eligible eye between Randomization visit date and End of Treatment date.
(from the eCRF form "Frequency of preservative free artificial tears use" forms)  |
| Total number of days of the treatment period  | End of Treatment date – Randomization date + 1   |
| Total number of drops of the
preservative free artificial tears
during the follow-up period | Sum of Morning/Afternoon/Evening Number of drops taken after End of Treatment date.
(from the eCRF form "Frequency of preservative free artificial tears use" forms)  |
| Total number of days of the follow-up period  | Last follow-up available visit* date – End of Treatment date + 1
(* with assessment of Frequency of preservative free artificial tears use)   |
| Time from randomization to study discontinuation (days)   | End of Study date – Randomization date + 1   |
| Primary and Secondary Sjögren's   | For the subgroup analyses, a patient will be classified as primary Sjögren's syndrome if the patient experienced any previous and/or concomitant ocular with diagnosis='Sjogren Syndrome'. Otherwise the patient will be classified as secondary Sjögren's syndrome                |
| Conversion of Time Intervals  | If a time interval was calculated in minutes, hours or days and needs to be converted into months or year the following conversion factors will be used:
• 1 hour = 60 minutes
• 1 day = 24 hours
• 1 week = 7 days
• 1 month = 30.4375 days
• 1 year = 365.25 days |
| General rule  | For calculation of a time interval, in case time is available, it is considered in the formula. Time intervals will be expressed in hours in if less than 24 hours and days if more than 24 hours.   |

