# 4.1. INCLUSION CRITERIA

To be eligible for inclusion into this study, each patient must fulfil the following inclusion criteria:

- 1. Male or female aged  $\geq 18$  years
- 2. Patients with a confirmed diagnosis of Sjögren's syndrome or other autoimmune disease known to induce Sjögren's DED.
- 3. Patients with severe Sjögren's DED characterized by the following clinical features:
  - a. Corneal and/or conjunctival staining with fluorescein using National Eye Institute (NEI) grading system  $\geq 3$
  - b. SANDE questionnaire >25 mm
  - c. Schirmer test I (without anaesthesia)  $\ge 2 \le 5$ mm/5min
- 4. The same eye (eligible eye) must fulfill all the above criteria
- 5. Patients diagnosed with severe Sjögren's DED at least 3 months before enrolment (current use or recommended use of artificial tears for the treatment of Sjogren's related DE)
- 6. Best corrected distance visual acuity (BCDVA) score of  $\geq 0.1$  decimal units (20/200 Snellen value) in each eye at the time of study enrolment
- 7. If a female of childbearing potential, have a negative urine pregnancy test and use a highly effective method to avoid pregnancy for the duration of the trial and 30 days after the study treatment period . Males of reproductive potential should use effective contraception during treatment and 30 days after the study treatment period
- 8. Patients who have given written informed consent before any study-related procedures not part of standard medical care are performed.
- 9. Patients must have the ability and willingness to comply with study procedures.
- **10.** Patients under treatment with topical cyclosporine (CsA), or topical ophthalmic treatments of the same class for at least 30 days before screening visit (day -8).

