# 4.2. ELIGIBLE EYE

Should all the inclusion/exclusion criteria be met in both eyes, the worse eye (eligible eye) will be determined **at the baseline visit using** a stepladder approach, as follows:

- 1. Schirmer's Test (since this is the primary endpoint)-Worse eye will be determined as eye with lower Schirmer I score.
- 2. NEI score (cornea+conjunctival staining) If Schirmer I score is the same in both eyes, worse eye will be determined by NEI score (cornea+conjunctival staining).

If all of the above are identical, determination of the worse eye will be based on the Investigator's judgement, otherwise **simply use the right eye** as the eligible eye.

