# 8.7 Dry Eye History

The dry eye history characteristics will be summarized by treatment and overall, by means of descriptive statistics. No statistical testing will be carried out. The following information will be reported:

- Eye affected by Dry Eye.
- Time since first diagnosis of Dry Eye.
- Has the patient received prior treatment for dry eye?
- Eye diagnosed with Severe Sjögren's Dry Eye.
- Time since first diagnosis of Severe Sjögren's Dry Eye.

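### SAP Table 3 selects the eligible eye through a diagnosis answer and does not check each eye's baseline values, so coded as written it can analyse an eye that fails the entry criteria

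*SAP*

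**What the plan says.** Protocol 4.1 defines severe disease by criteria 3a (NEI staining of at least 3), 3b (SANDE above 25 mm) and 3c (Schirmer I from 2 to 5 mm). Criterion 4 adds: "The same eye (eligible eye) must fulfill all the above criteria". One qualifying eye is therefore enough for entry, and that eye is the eligible eye. Protocol 4.2 covers the case of two qualifying eyes: "Should all the inclusion/exclusion criteria be met in both eyes, the worse eye (eligible eye) will be determined" at the baseline visit, first by lower Schirmer I and then by NEI. SAP 4.7 repeats this condition, including the restriction to both eyes.

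SAP 12.1, Table 3, is the derivation a programmer would follow. It opens with "Assuming that all the inclusion/exclusion criteria are met" and leaves out the restriction to both eyes. The bilateral branch begins "If both eyes fulfill the criteria of Severe Sjögren's Dry Eye". A parenthesis then says how this is recognised: the item on which eye is diagnosed "is answered with 'Both') than the eligible eye will be selected according to the following rank". The first rank is "the eye with lower Schirmer I score, otherwise". If the item names one eye, that eye is taken. SAP 8.7 lists "Eye diagnosed with Severe Sjögren's Dry Eye" under Dry Eye History, beside the time since that diagnosis. SAP 7.9, which lists changes from the protocol, does not mention the eligible-eye rule.

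**The concern.** The Table 3 test for whether both eyes qualify is a diagnosis answer, not the measurements that define qualification. Inclusion criterion 5 requires the diagnosis at least 3 months before enrolment, and Table 3 uses a diagnosis date for each patient's eligible eye. A diagnosis of that age does not show that an eye measured 2-5 mm at baseline.

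The synopsis defines the Schirmer co-primary in the eligible eye, and SAP 9.1 computes compliance in it. If the derivation picks the wrong eye, the response and the baseline Schirmer covariate come from an eye other than the one that qualified the patient. The estimand population in SAP 7.3 is defined by the entry criteria, but the analysed eye could lie outside them. Such a patient is validly enrolled on the other eye, so a check of patient-level eligibility would not reveal the problem.

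**Working it through.** **1. The rules compared**

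| Step | Protocol 4.2 and SAP 4.7 | SAP Table 3 |
|---|---|---|
| Condition for the ladder | All criteria met in both eyes | Both eyes fulfil the disease criteria, recognised by the answer *Both* |
| Check of each eye's Schirmer I and NEI | Implied by the condition | None stated |
| First rank | Lower Schirmer I | Lower Schirmer I, no 2 mm floor |
| Only one eye qualifies | That eye (criterion 4) | The eye named in the diagnosis item |

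**2. Which eye Table 3 returns**

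Take a patient with one qualifying eye at 2, 3, 4 or 5 mm and the answer *Both*, and vary the fellow eye.

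- Fellow eye at 0 or 1 mm: it is always lower, so it is always selected, and it fails criterion 3c. Example: right 4 mm, left 1 mm gives the left eye.
- Fellow eye at 2-4 mm and lower than the qualifying eye: it is selected. It fails criterion 3a if its NEI is below 3.
- Fellow eye above 5 mm: never selected. In this branch the Schirmer breach is at the low end only.

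In the one-eye branch the named eye is taken unchecked, so it could fall on either side of the range if the other eye was the one that qualified.

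**3. The plan's own power**

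Inputs from SAP 5: vehicle response 0.33, difference 0.42 (so cenegermin 0.75), 72 evaluable patients (36 per arm), one-sided alpha 0.025.

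Power = Φ[(p1 − p0 − 1.96·SE0)/SE1], with SE0 = √(2·p̄(1−p̄)/36), p̄ = (p0+p1)/2, and SE1 = √([p0(1−p0) + p1(1−p1)]/36).

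Here p̄ = 0.54, SE0 = 0.1175 and SE1 = 0.1065. Then (0.42 − 1.96 × 0.1175)/0.1065 = 1.78, and power = 96.3%. This is the SAP's figure. The sample-size calculation is not in error.

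**4. Possible effect on Schirmer power**

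The documents give no between-eye Schirmer distribution and no response rate by baseline Schirmer value, so both inputs are assumptions. Let a share f of analysed eyes be below 2 mm, responding at h times the planned rate in each arm. Both rates are then multiplied by k = 1 − f + f·h.

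| f | h = 1 (full effect kept) | h = 0.5: rates and difference | h = 0.5: power |
|---|---|---|---|
| 10% | 96.3% | 0.3135 vs 0.7125, 39.9 points | 94.0% |
| 20% | 96.3% | 0.297 vs 0.675, 37.8 points | 91.1% |
| 30% | 96.3% | 0.2805 vs 0.6375, 35.7 points | 87.6% |

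As an outer bound, if no such eye could pass 10 mm in either arm (h = 0), power would be 91.1%, 83.5% and 74.0%.

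**The case against.** The bilateral branch of Table 3 does not start with the questionnaire answer. It starts with both eyes fulfilling the criteria of severe disease, and the protocol defines severe disease by 3a-3c. Read that way, an eye at 0-1 mm never enters the ladder. SAP 4.7 states the condition correctly. A reader might infer that the SAP meant to depart from the protocol; the documents do not support that.

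A reader might also infer that the diagnosis item records history alone. That cannot be confirmed: the CRF is not among the documents, and SAP 8.7 lists the eye affected by dry eye separately from the eye diagnosed with severe Sjögren's dry eye, so sites may have been told to use the trial's definition. The section heading and the attached diagnosis date make the history reading plausible, not certain.

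Finally, the claim that eyes below 2 mm can hardly pass 10 mm has no source in the documents. They may lie only 1 mm below the entry floor, and if they keep the full effect no power is lost.

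These points limit the finding but do not remove it. Table 3 names a specific test for its condition, that test does not look at the measurements, and nothing later in the rule does. SAP 8.2 provides for case-by-case review of protocol deviations before unblinding, but does not say that the eligible eye is re-derived.

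**Conclusion.** The point holds as a conflict between Table 3 on one side and SAP 4.7, protocol 4.2 and inclusion criteria 3 and 4 on the other. Coded as written, Table 3 can return a fellow eye at 0-1 mm, or a lower-Schirmer eye with NEI below 3, in place of the eye that qualified the patient. Whether it does so in practice depends on how sites completed the diagnosis item and how often the two eyes differ; neither is known.

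The Schirmer co-primary is the main endpoint exposed. SANDE, as described in SAP 12.2, is not eye-specific. SAP 7.1 says only that some endpoints use the eligible eye, so the reach to other signs is less certain. A reader might infer bias towards one arm. The documents do not support that: the rule uses baseline data and is identical in both arms, so it changes the analysed population, the baseline covariate and possibly power, but does not by itself favour an arm.

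Nor can a definite loss of power be claimed. Under the assumed 10-30% share, the result runs from no loss (about 96%) to 94%-88% at half the planned rates. The matter should be corrected before unblinding because the rule can choose the wrong analysis eye for a co-primary endpoint and is easy to change.

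**What to change.** In Table 3, replace the diagnosis answer with eligibility derived for each eye:

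1. An eye qualifies if its baseline Schirmer I is 2-5 mm and its baseline NEI is at least 3, using the values on which entry was decided. State whether NEI comes from the site or the reading center, since SAP 7.8 prefers the reading center for analysis.
2. If one eye qualifies, take it. If both qualify, apply the ladder as in SAP 4.7 and protocol 4.2.
3. If no eye qualifies at baseline in a FAS patient, take the eye that qualified at screening, or else apply the ladder across both eyes. This fallback is needed because the FAS keeps every randomized and treated patient.
4. At the blind data review, list every patient in whom this derivation and the diagnosis-item rule disagree, and settle those cases before unblinding.

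The cost is one derivation rule and one listing. The protocol's baseline visit already measures Schirmer I and NEI in both eyes, so no new data are needed.
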